• CPRD Aurum: 39,043,877 participants ever contributing data to 1,485 GP practices using the EMIS GP software.

Both Gold and Aurum databases include information on patient demographics, lifestyle factors, diagnoses, and results of investigations including blood tests, hospital referral, and details of all GP prescriptions [35]. The medication data includes information about dose

and date of prescription and are stored as product codes mapped onto British National Formulary codes in the CPRD Gold and the Dictionary of Medicines and Devices in the CPRD Aurum.

Diagnostic and clinical data in the CPRD Gold are recorded as medical Read codes whereas these data are stored using a mixture of Read version 2, SNOMED and local EMIS[®] codes in the CPRD Aurum database [36]. Diagnosis, prescription, test and observation (e.g. BMI) data in CPRD Gold are stored in the clinical, therapy, test and additional files respectively. Data for diagnosis, test results and observations such as BMI are stored in the observation file of CPRD Aurum, while prescription data are stored in drug issue file.

The data in the CPRD undergo thorough quality checks and are of a reliable research standard with a high validity of recorded diagnoses, including a median proportion of cases with a confirmed diagnosis of 89% for 183 different conditions including chronic auto-immune diseases [37].

We will develop the prediction model for Mesalazine, Sulfasalazine, Azathioprine and Mycophenolate using data from CPRD Aurum, and externally validate using data from CPRD Gold as the former has substantially more participants.

For methotrexate, we will use CPRD Gold for model development as (a) this was approved in the previous ISAC application and we are at advanced stages of model building for this drug, (b) there were 1,262 outcome events for patients with autoimmune rheumatic diseases prescribed methotrexate in CPRD Gold providing adequate power, and (c) inclusion of participants with psoriasis or inflammatory bowel disease (proposed in the current application) will further increase the power.

Approximately 200 general practices that have moved from Vision to EMIS GP software have contributed data to both platforms. However, these practices are identified by CPRD in a bridging file, and will be excluded from the validation cohort.

Study start date: 01/01/2007 Study end date: 31/12/2019

Cohort entry and start of follow-up: At first prescription and day 180 of the first primarycare prescription of a drug of interest respectively. Separate cohorts will be built for each drug.

Cohort exit: Earliest of target-organ adverse event, drug discontinuation, death, moving to a different practice, 5-year follow-up time, or 31/12/2019 (study end date).

Inclusion criteria:

[1] Diagnosis of any common inflammatory disease i.e. RA, inflammatory bowel disease, psoriasis +/- arthritis, ankylosing spondylitis, systemic lupus erythematosus, or reactive arthritis. These are the commonest inflammatory conditions treated with immune-suppressive drugs.

[2] Age ≥18 years at diagnosis.

[3] At least one GP prescription of methotrexate, azathioprine (or mercaptopurine), aminosalicylates, sulfasalazine, mycophenolate. These are the most commonly prescribed immune-suppressing drugs for which blood test monitoring is recommended.
[4] Meeting CPRD data quality standards (UTS for Gold and acceptable flag for Aurum) and with a continuous registration for at least one year before the first date of diagnosis of inflammatory disease in CPRD Gold and CPRD Aurum.

The requirement to have one-year disease free registration in the CPRD prior to first date of inflammatory disease diagnosis is to allow for the identification of incident cases, and those newly commenced on immune-suppressing drugs. This will exclude prevalent cases of inflammatory diseases on long-term hospital prescribed immune-suppressive drugs who have recently switched to GP prescription due to implementation of primary-care/secondary-care shared care prescribing in their area.

Exclusion criteria: Presence of any of the below prior to cohort entry:

[1] eGFR < 15 ml/min or chronic kidney disease stage 4 or 5.

[2] Chronic liver disease: Autoimmune hepatitis, hepatitis B or C, cirrhosis

[3] Pre-existing hematological abnormalities: Myelodysplasia, primary hematological diseases causing neutropenia or thrombocytopenia.

[4] Prescription of the immunosuppressive drugs listed above before first inflammatory disease diagnosis date.

[5] Registered in GP practices not meeting CPRD data quality standard at cohort entry.

Selection of comparison group(s) or controls

A comparison group is not applicable in the context of risk prediction modelling. Exposures, outcomes and covariates

Predictors of drug discontinuation: Candidate prognostic factors will be identified using two approaches:

[1] Theory driven based on prior knowledge: A list of recognised prognostic factors for abnormal monitoring blood test results have been developed based on the research teams' clinical experience. The a priori agreed prognostic factors include: age, sex, body mass index, alcohol consumption, smoking, CKD stage 3, type 2 diabetes, and prescription of selected drugs that increase risk of acute kidney injury or transaminase elevation at baseline.

[2] Evidence based, based on systematic review: A systematic review of existing literature is currently underway to identify other prognostic factors. This will provide additional candidate predictors (PROSPERO: CRD42020208049).

The presence of comorbid and lifestyle prognostic factors will be ascertained using primarycare diagnoses and lifestyle data collected in the two-years preceding cohort entry. The presence of prescription prognostic factors will be ascertained using primary-care prescriptions in the 180 days preceding cohort entry.

Outcomes

Primary outcome: Target organ specific adverse event resulting in drug discontinuation from 6 months of initial primary-care prescription to until 5-years after the initial prescription.

This will be defined as drug discontinuation with either (a) diagnosed with target organ damage based on clinical code, or (b) significant abnormal blood test results.

Drug discontinuation due to abnormal monitoring blood test results will be defined as present when there is:

(a) a gap between two prescriptions, or between last prescription date and earliest of death date, moving to a different practice, 5-year follow-up time, or 31/12/2019 (study end date) of \geq 90 days, and

(b) an abnormal blood-test result in the 15 days preceding or 45 days after the last prescription date. The 15-day preceding window is to allow for any delay in acting on abnormal blood-test results.

Abnormal blood test results will be defined according to the British Society for Rheumatology DMARD monitoring guidelines 1, and CKD progression will be defined as per the Kidney Disease Improving Global Outcomes guideline 20122:

- White blood cells <3.5x109/L,
- Neutrophils <1.6x109/L,
- Platelets <140x109/L,
- Alanine Transaminase and/or Aspartate Transaminase >100 units/L,

• CKD progression defined as creatinine difference > 26 micro mol/L above the first or second preceding result or chronic kidney disease stage progression.

In addition, in people with psoriasis (but without arthritis), methotrexate discontinuation will be defined to be due to blood-test abnormalities if (i) serum amino-terminal propeptide of type III procollagen (PIIINP) is > 8 mg/L on two previous occasions; (ii) if three previous PIIINP measurements were >4.2 mg/L in the previous 12-month period; or (iii) if previous PIIINP measurement was > 10 mg/L as per guidelines for the the British Association of Dermatologists [3].

Primary outcome identification: Study participants who have the outcome of interest will be identified as follows:

Step 1: All participants with drug discontinuation as defined above will be identified.

Step 2: The results of their blood tests from up to 15 days before and 45 days after the last DMARD prescription date, and the dates of blood tests will be extracted.

Step 3: All other Read code entries in the clinical and investigation files indicating abnormal blood test results within this 60-day period (-15 to + 45 days), and the date of such entry will be extracted.

Step 4: Participants with abnormal blood test results or a Read code specifying abnormal blood test results within this period and their date of event will be ascertained.

Secondary outcome: Drug discontinuation due to any reason. Defined as a gap between two prescriptions, or between last prescription date and earliest of death date, moving to a different practice, 5-year follow-up time, or 31/12/2019 (study end date) of \geq 90 days. Data/statistical analysis

Mean (standard deviation), and n (%) will be used for descriptive purposes.

Derivation and validation of the risk prediction model:

The theory driven and systematic review derived prognostic factors will be included in a flexible parametric survival model, to identify the prognostic factors (predictors) of the outcomes of interest i.e. target organ specific adverse events or drug discontinuation due to abnormal monitoring blood test results. Multiple imputation using chained equations will be used to deal with missing data. The number of imputations will depend on the extent of missing data. All of the data available in the CPRD Aurum (except for methotrexate where we will continue to use CPRD Gold for model development) will be used to develop the risk prediction model. All candidate predictors will be included. We will form the risk equation for the outcome of interest by a function of the estimated β coefficients multiplied by values of the corresponding predictors included in our model together with the baseline hazard function. This process ultimately leads to an equation for the predicted absolute risk over time. We will examine the performance of this final model in terms of discrimination by calculating the c-statistic and calibration by plotting agreement between predicted and observed risks across the whole range of predicted risk at relevant time-points (calibration plot with smoothed calibration curves, with measures of calibration-in-the-large and calibration slope, as estimated using pseudo-observations). As part of the process of internal validation, to account for optimism caused by over-fitting, for each imputation separately, we will develop a model separately within 100 samples of the derivation data with replacement of the same size of the original sample (bootstrap samples). From this the optimism will be estimated by comparing the performance of the model in the bootstrap samples with the same model in the original sample. We will then estimate the overall optimism averaged over all 100 models in each imputed dataset and estimate a uniform shrinkage factor, equal to the average of the calibration slopes from each of the bootstrap samples. The process will be repeated for each imputed dataset, and the final uniform shrinkage calculated by averaging across the estimated shrinkage estimates from the imputations. Then, to account for over-fitting during the development process, we will multiply (penalize) the original β coefficients by the uniform shrinkage factor. At this point, the baseline hazard will be re-estimated on the basis of the shrunken β coefficients to ensure that overall calibration is maintained, producing a final model. Outcomes affected by competing events (e.g. discontinuation due to renal or liver abnormalities) will be accounted for using a competing risks and multi-stage modelling framework, within the flexible parametric framework via a subdistribution (Fine and Gray) approach [38]. Continuous predictors will not be categorised and potential non-linear effects examined using fractional polynomials.

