Incidence of drug discontinuation: Survival analysis will be undertaken to calculate the incidence rate of drug discontinuation (95% confidence intervals (CI)) per 1,000 personyears for entire study period, first 12-months of follow-up, and the subsequent period. Life tables will be constructed to estimate the cumulative incidence at 1-year and 5-year follow-up. Cumulative hazards will be plotted using Nelson-Aalen graphs. Data management and analysis will be performed in Stata MP v16.

Plan for addressing confounding

Bias due to transferring GP surgeries: To minimise bias due to prevalent users appearing as incident users in a new GP surgery, data for participants who receive a prescription of a DMARD within one year of their current registration in a GP surgery will be excluded from the cohort. This will minimise the chance of prevalent long-term users of these medicines entering the cohort as new incident-users.

Plans for addressing missing data

Multiple imputation using chained equations will be used to deal with missing data. We expect BMI, alcohol intake, smoking and ethnicity to have missing values. The number of imputations will depend on the extent of the missing data.

Missing data on blood test results: The CPRD has data about blood test results. However, it is possible that in some instances of drug discontinuation due to abnormal monitoring blood test results, the numerical blood test results are not available in the CPRD. However, just as

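### A two-year look-back ending at the first prescription would miss lasting diagnoses (type 2 diabetes, CKD stage 3) coded only earlier, or first coded before day 180

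*Protocol*

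**What the plan says.** Under *Exposures, outcomes and covariates*, the protocol lists the a priori predictors as "age, sex, body mass index, alcohol consumption, smoking, CKD stage 3, type 2 diabetes, and prescription of selected drugs" that raise the risk of kidney injury or transaminase elevation. It then sets a single rule for all comorbid and lifestyle factors: "The presence of comorbid and lifestyle prognostic factors will be ascertained using primarycare diagnoses and lifestyle data collected in the two-years preceding cohort entry". No exception is made for lasting conditions.

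The anchor of that window is defined under *Definition of the study population*, where cohort entry and start of follow-up are placed "At first prescription and day 180 of the first primarycare prescription of a drug of interest respectively". The look-back thus ends about six months before prediction begins. Objective 1, in both the *Technical summary* and *Objectives, specific aims and rationale*, instead conditions on prognostic factors available at six months of prescription.

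The exclusion criteria carry no time limit: "Presence of any of the below prior to cohort entry". The renal one reads "eGFR < 15 ml/min or chronic kidney disease stage 4 or 5".

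On missing data, the protocol says: "We expect BMI, alcohol intake, smoking and ethnicity to have missing values". Comorbidities are not in that list.

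**The concern.** A diagnosis of type 2 diabetes or CKD stage 3 does not lapse because it was coded three years ago. A two-year window suits quantities that change, such as BMI, smoking and alcohol, but for a lasting condition it can turn an old code into an apparent absence. Multiple imputation would not help, because a present/absent indicator built from codes leaves no gap to impute.

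What is at stake is the predicted risk of the individuals who are missed. The model is meant to support a risk threshold above which patients are monitored frequently (decision curve analysis under *Data/statistical analysis*). A patient with long-standing diabetes scored as non-diabetic gets too low a risk and may fall below that threshold.

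**Working it through.** **The rules side by side**

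| Item | Records that count |
|---|---|
| Comorbid predictors | Two years ending at the first prescription |
| Exclusions | Any time before the first prescription |
| Objective 1 | Factors available at six months of prescription |

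Two consequences follow. A stage 4 code from five years before entry excludes a patient, while a stage 3 code of the same age does not count as CKD stage 3. A diabetes code first entered on day 100 is available when prediction starts on day 180, yet it is not used.

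**Size (illustration only).** The plan states no figure on this point: no prevalence, no share of codes falling inside the window and no hazard ratio. All three are assumed here.

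- p = true prevalence (5-15%)
- s = share of affected patients with a code inside the window (50-90%)
- HR = true hazard ratio (1.5-3.0)

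The formulas treat one predictor alone and assume that missed and captured patients have the same true hazard.

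- Share of all patients affected but missed: p(1 − s)
- Share of the apparently unaffected group that is truly affected: c = p(1 − s)/(1 − ps)
- Mean hazard in that group, relative to the truly unaffected: h = 1 − c + c·HR
- Estimated hazard ratio: approximately HR/h
- Predicted over true risk for a missed patient: approximately h/HR

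Worked case, p = 0.10, s = 0.5, HR = 1.5:

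- c = 0.05/0.95 = 0.053
- h = 1 + 0.053 × 0.5 = 1.026
- estimated hazard ratio = 1.5/1.026 = 1.46
- missed patient = 1.026/1.5 = 0.68 of true risk

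Corners of the range:

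| p | s | HR | Missed, share of all | c | Estimated HR | Estimated/true HR | Missed patient, predicted/true |
|---|---|---|---|---|---|---|---|
| 0.05 | 0.9 | 1.5 | 0.5% | 0.005 | 1.496 | 0.997 | 0.668 |
| 0.05 | 0.9 | 3.0 | 0.5% | 0.005 | 2.969 | 0.990 | 0.337 |
| 0.15 | 0.5 | 1.5 | 7.5% | 0.081 | 1.442 | 0.961 | 0.694 |
| 0.15 | 0.5 | 3.0 | 7.5% | 0.081 | 2.581 | 0.860 | 0.387 |

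The coefficient changes little, while the missed individuals are scored at 0.34-0.69 of their true risk.

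**Renal exclusion.** The protocol does not define CKD stages numerically or say whether stage is read from codes, from eGFR or from both. Assume that stage 4 covers some eGFR values of 15 and above.

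- Stage from codes only: a patient with an eGFR in that range and no stage 4 code stays in the cohort and, without a stage 3 code in the window, counts as not CKD stage 3.
- Stage may be derived from eGFR: the patient is excluded as stage 4, the numeric limit is merely redundant, and nobody is misplaced.

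**The case against.** The strongest reply is that the effect may be small. That these conditions are often coded once and not again is an assumption from outside the documents; if practices re-enter the codes regularly, few patients are missed. The protocol also does not state outright that no code means absent. Other predictors (age, BMI, prescriptions) may recover part of the missed risk where they are correlated with it. These points stand, and they limit what can be said about size. They do not change what the written rule does to a patient whose only code lies outside the window.

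A fixed window also has a real advantage: it gives everyone the same look-back. The protocol guarantees only "continuous registration for at least one year before the first date of diagnosis of inflammatory disease", so an unlimited look-back would vary with record length. That is a fair cost of the change.

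A reader might go further and infer that the coefficients would reflect recency of coding more than disease. The figures above do not support that: the estimated hazard ratio keeps at least 86% of its value throughout the assumed range. A reader might also infer that performance would differ between Gold and Aurum because coding habits differ. The documents give no evidence of this. They plan a common code search strategy, external validation in the other database and cluster-specific checks.

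**Conclusion.** The point holds for the look-back. Followed as written, the rule does not count a lasting diagnosis coded only before the two-year window, or first coded in the 180 days after the first prescription. The latter conflicts with the stated objective of using what is known at six months. The number affected is unknown. Under the assumed ranges the harm falls on the missed individuals (predicted at roughly 0.34-0.69 of true risk, before any recovery through correlated predictors) and hardly on the coefficient. Reading an absent code as absence of disease is an inference, though the natural one given how presence is defined.

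The renal exclusion supports a query only. It is tempting to conclude that severe uncoded kidney disease ends up in the reference group. The text does not establish this: anyone with an eGFR below 15 is excluded by the numeric limit, coded or not, and patients between the two limits are misplaced only if stage is read from codes alone.

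**What to change.** State that lasting diagnoses (type 2 diabetes, CKD stage 3 and any other permanent comorbidity added from the systematic review) are ascertained from any record up to the start of follow-up at day 180. Keep the two-year window for BMI, smoking and alcohol. State explicitly that no code in the permitted period is treated as absence.

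State whether CKD stage is taken from codes, eGFR values or both, and reconcile the renal exclusion with the CKD predictor so that every patient's renal category is defined.

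The cost is a wording change and a wider date range in the extraction. The number of candidate parameters stays at 50, so the stated requirement of 16,416 participants and 329 events is unaffected. Two downsides should be accepted openly. Look-back length will vary with registration history, which a sensitivity analysis using the fixed two-year window can check. The methotrexate extraction, where the protocol describes model building as advanced, must be re-run.

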Question: What is the optimum strategy of blood testing after the first six months of primary-care immune-suppressing drug prescription?

Objectives: [1] Develop and validate a prediction model for estimating an individual's risk of target-organ damage conditional on their values of multiple prognostic factors available at 6 months of primary-care immune-suppressing drug prescription, [2] Identify incidence of drug discontinuation for any reason, and due to abnormal monitoring blood test results in each year of prescription.

Methods: Data from Clinical Practice Research Datalink (CPRD) Gold and Aurum will be used. We will utilise CPRD-HES linked data to validate the sensitivity of outcome definition in primary-care data alone.

People with common inflammatory conditions treated with immune-suppressing drugs, will be followed up electronically from day 180 of the first primary-care prescription of a drug of interest until the earliest of target-organ adverse event, drug discontinuation, death, moving to a different practice, 5-year follow-up time, or 31/12/2019 (study end date).

A penalized flexible parametric survival model will be used to develop a risk prediction score for drug discontinuation due to target organ damage using CPRD Aurum given its larger sample size, accounting for competing risks as necessary, and with internal validation using bootstrapping to quantify and adjust for optimism. The predictive performance of the score will be validated in CPRD Gold. GP practices contributing data to both CPRD Aurum and GOLD will be excluded from the validation cohort. Separate risk scores will be developed and validated for each drug of interest. Risk thresholds will be agreed using decision curve analysis and with patient and clinician involvement. Incidence (per 1,000 person-years) of treatment discontinuation in each 12-month of primary-care prescription will be estimated.

Outcomes to be measured

Primary outcome: Drug discontinuation due to target organ specific adverse event. This will be defined as drug discontinuation with either (a) abnormal blood test results due to target-organ damage, or (b) target organ damage based on clinical code allocation.

Drug discontinuation due to abnormal monitoring blood test results will be defined as present when there is:

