(a) a gap between two prescriptions, or between the last prescription date and earliest of death date, moving to a different practice, 5-year follow-up time, or 31/12/2019 (study end date) of \geq 90 days, and

(b) the last prescription is preceded in up to 15 days by abnormal blood test results (to account for any delay in acting on abnormal results) or followed by an abnormal test result in the next 45 days.

Abnormal blood test results will be defined according to the British Society for Rheumatology DMARD monitoring guidelines1, and CKD progression will be defined as per the Kidney Disease Improving Global Outcomes guideline 20122:

- White blood cells <3.5x109/L,
- Neutrophils <1.6x109/L,
- Platelets <140x109/L,
- Alanine Transaminase and/or Aspartate Transaminase >100 units/L,

• CKD progression defined as creatinine difference > 26 micro mol/L above the first or second preceding blood-test result or chronic kidney disease stage progression.

In addition to the above blood-test abnormalities, in people with psoriasis, methotrexate discontinuation will be defined to be due to blood-test abnormalities if (i) serum amino-terminal pro-peptide of type III procollagen (PIIINP) is > 8 mg/L on two previous occasions; (ii) if three previous PIIINP measurements were >4.2 mg/L in the previous 12-month period; or (iii) if previous PIIINP measurement was > 10 mg/L as per guidelines for the British Association of Dermatologists [3].

Secondary outcome: Drug discontinuation due to any reason.

Defined as present if there is a gap between two prescriptions, or between last prescription date and earliest of death date, moving to a different practice, 5-year follow-up time, or 31/12/2019 (study end date) of ≥ 90 days.

Objectives, specific aims and rationale

The overall purpose of this study is to ascertain the optimum strategy of blood testing for adults with common inflammatory conditions treated with immune-suppressing drugs after the first six months of primary-care prescription. By strategy we mean the optimum frequency of testing, and how the frequency of testing should alter according to the individual's risk.

The objectives are to:

[1] Develop and validate a prediction model estimating an individual's risk of target-organ damage conditional on their values of multiple prognostic factors available at six months of immune-suppressing drug prescription.

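### Comorbidity, lifestyle and co-prescription predictors are read before the first prescription (day 0), but the model is meant to predict at six months (day 180)

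*Protocol*

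**What the plan says.** The protocol defines two separate dates under the definition of the study population: "Cohort entry and start of follow-up: At first prescription and day 180 of the first primarycare prescription of a drug of interest respectively". Cohort entry is therefore day 0 and the start of follow-up is day 180. The technical summary agrees, saying that patients "will be followed up electronically from day 180 of the first primary-care prescription of a drug of interest". The primary outcome runs "from 6 months of initial primary-care prescription to until 5-years after the initial prescription".

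Objective 1 sets the prediction time at the same six-month point. The technical summary conditions the risk on "values of multiple prognostic factors available at 6 months of primary-care immune-suppressing drug prescription", and the section on objectives, specific aims and rationale repeats this: "conditional on their values of multiple prognostic factors available at six months of immune-suppressing drug prescription".

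The section on exposures, outcomes and covariates then ties the predictor windows to the earlier date. Comorbid and lifestyle factors come from diagnoses and "lifestyle data collected in the two-years preceding cohort entry". For co-medication: "The presence of prescription prognostic factors will be ascertained using primary-care prescriptions in the 180 days preceding cohort entry". The same section also refers to baseline for co-prescriptions, but the protocol does not define that word, and nowhere does it update predictors at day 180.

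**The concern.** A prognostic model should use predictor information up to the moment at which the prediction is made. Here that moment is day 180, yet the stated windows close on day 0. The interval left out is an eventful one: the study background says that side-effects generally occur within the first six months, under frequent testing. During it a patient may start or stop a drug that raises the risk of kidney injury or transaminase elevation, or have CKD stage 3 or diabetes newly recorded.

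Two things are at stake. First, coefficients estimated on pre-treatment status would understate the association with six-month status for predictors that change. Second, a clinician using the score at six months would most naturally enter current values, which are not the values on which the model was fitted. The protocol gives no different predictor timing for the validation database, so good external calibration would show that the model works with day-0 inputs and not that it works with current inputs. Risk thresholds from these models feed the cost-effectiveness analysis of testing frequency.

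**Working it through.** **Date arithmetic.** The protocol states no figure to reproduce on this point. The check re-expresses each window relative to the start of follow-up.

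Inputs, all from the protocol: cohort entry = day 0; start of follow-up = day 180; prescription window = 180 days before cohort entry; comorbidity and lifestyle window = two years (about 730 days) before cohort entry.

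Formula: day relative to prediction time = day relative to cohort entry - 180.

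- Prescription window: from -180 - 180 = -360 to 0 - 180 = -180.
- Comorbidity and lifestyle window: from -730 - 180 = about -910 to 0 - 180 = -180.

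So prescription data are 180 to 360 days old at the prediction time, and comorbidity and lifestyle data 180 to about 910 days old. With the windows anchored at day 180, the prescription window would run from day 0 to day 180 of treatment, the comorbidity and lifestyle window from about day -550 (180 - 730) to day 180, and the gap before the prediction time would be zero.

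**Illustration of attenuation.** The inputs here are assumptions, because the protocol gives no rate of change for any predictor. Take one binary co-prescription with a true hazard ratio of 1.5 for status at day 180, a hazard of 1 if unexposed, and no other covariates.

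*Starters and stoppers in equal number.* 30% are exposed at both dates, and 20% of day-180 users are starters. Starters are then 0.20 x 30% = 6% of the cohort, and stoppers also 6%.

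- Coded exposed at day 0: 0.8 x 1.5 + 0.2 x 1 = 1.40.
- Coded unexposed at day 0: (0.06 x 1.5 + 0.64 x 1)/0.70 = 0.73/0.70 = 1.043.
- Fitted ratio: 1.40/1.043 = 1.34, against a true 1.5.
- If current status is entered at six months, an exposed patient is scored at 1.40/1.50 = 0.93 of the true hazard and an unexposed patient at 1.043 of it.
- With zero turnover the fitted ratio stays at 1.50.

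*Starters only, nobody stops.* Again 20% of day-180 users are new, with day-180 prevalence p between 10% and 50%. The coded-unexposed hazard is 1 + 0.5 x 0.2p/(1 - 0.8p).

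- p = 10%: 1 + 0.01/0.92 = 1.011; fitted ratio 1.5/1.011 = 1.48.
- p = 50%: 1 + 0.05/0.60 = 1.083; fitted ratio 1.5/1.083 = 1.38.

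**The case against.** The strongest reply is that objective 1 asks for values available at six months, not measured at six months, and a pre-treatment record is still available then. A model fitted on day-0 values and used with day-0 values is internally consistent; it merely uses older information. The harm at the point of use needs the further step that users enter current values, and the protocol describes no input procedure. This stands as a limit on the claim: the model would not be invalid in itself. It does not remove the conflict, because the windows shut out newer values that are equally available at six months, and the stated purpose is a decision taken at that time.

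Further limits also stand. CKD stage 3, diabetes, smoking and BMI are unlikely to change much over six months for most people, so co-prescriptions are the main item affected. Sex is unaffected, and a day-0 age differs from age at day 180 only by a fixed half year.

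A reader might infer two stronger things. One is that monitoring blood results from the first six months are barred as predictors. The text does not show this: windows are set only for comorbidity, lifestyle and prescription factors, and none for the predictors that the systematic review may add. Whether to add such results is a modelling preference and not part of this point. The other is that predictions would be about a third too low (1 - 1/1.5 = 33%). That figure does not depend on how many patients start a drug. It is close to the shortfall for an individual starter scored on day-0 status, which in the starters-only example is 33% (1 - 1.011/1.5) to 28% (1 - 1.083/1.5), in 2% to 10% of the cohort (0.2p). It is not a general error of the model.

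A statistical analysis plan may exist and was not available. The protocol does not leave the matter open, however: it fixes an explicit rule that conflicts with its own objective.

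**Conclusion.** The point holds. On the protocol's own definitions, the comorbidity, lifestyle and co-prescription windows close 180 days before the time at which the model is meant to predict, and nothing elsewhere repairs this. The 180-day gap is certain; it rests only on the stated dates.

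The effect on the coefficients is attenuation relative to six-month values, of a size that cannot be fixed from the protocol. Under the assumptions shown, a true hazard ratio of 1.5 would be fitted as somewhere between 1.50 (no turnover) and about 1.34 (20% turnover with equal starting and stopping). External validation with the same anchor would not test the score as applied with current values. Because the anchor governs every windowed predictor in each drug-specific model, it should be settled before extraction.

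**What to change.** In the section on exposures, outcomes and covariates, end the comorbidity, lifestyle and prescription windows at the start of follow-up (day 180) instead of at cohort entry, in both CPRD Aurum and CPRD Gold. Define baseline there as day 180. Keep the day-0 anchor for incident-user eligibility and the existing exclusions. Since risk time begins at day 180, predictor data up to that day precede all counted follow-up, so the change introduces no immortal time.

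No new data source is needed, and the sample size calculation is unchanged. The cost is re-extraction and refitting, notably for methotrexate, where the protocol says model building is already well advanced under an earlier approval. If re-anchoring is not done for that model, restate objective 1 for it as prediction from values before the first prescription, and specify that those are the values to be entered when the score is used.
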